## COGNITIVE SUBSTUDY AIMS

**AIM 1.** Compare the effects of a 4 month supervised HIIT or CME intervention on (1°) cognitive functioning (i.e., global and domain T scores and diagnoses of cognitive impairment) and (2°) subjective cognitive symptoms. We **hypothesize** that PWH randomized to HIIT will experience greater improvements in objective and subjective cognitive function compared to CME.

**Exploratory Aim 1.** Evaluate the biological mechanisms underlying HIIT and CME. We **hypothesize** that PWH randomized to HIIT will experience greater improvements in putative biomarkers underlying the effect of PA on cognition (blood markers: neurotrophins [e.g., BDNF], growth factors [e.g., VEGF], pro-inflammatory cytokines [e.g., IL-6] and neuroimaging markers: cerebral blood flow, resting state functional connectivity, and brain volume), which a particular focus on BDNF and cerebral blood flow, as they have demonstrated sensitivity to differences between HIIT and CME. Neuroimaging is UAB SITE ONLY.

**AIM 2.** Determine MoA of long-term PA maintenance at 12 months after a 4 month supervised HIIT or CME intervention AND a 3 month coaching or control texting intervention as parent of the parent study design. Distal predictors include sociodemographic (e.g., race, age, sex, education), clinical (e.g., physical health), and intervention factors (i.e., changes in parent R01 physical outcomes [cardiorespiratory fitness], condition [HIIT vs CME], [coaching vs control]). Proximal psychological MoA will be measured in real time with EMA (e.g., self-efficacy, perceived benefits, motivation, social support). We will also examine the extent to which habitual PA in daily life impacts durability of intervention-related cognitive and biomarker improvements from AIM 1.

**Impact:** As older PWH experience more comorbidities and complications, nonpharmacological approaches to improve physical function and alleviate symptoms of the growing population are urgently needed. The HEALTH study will generate scientifically rigorous data on physical function and fatigue responses to exercise, the associated mitochondrial adaptations, and investigate strategies to instill sustained, self-directed exercise behavior. These data will inform the development of scalable, effective exercise recommendations tailored to the unique needs of aging PWH.

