## F. Data Analysis Plan:

**Statistical Considerations.** We hypothesize that among older PWH, HIIT will lead to better physical function and reduced fatigue through improvements in mitochondrial bioenergetics compared with CME.

**Sample Size Calculations:** We assume a 1:1 randomization to HIIT or CME balanced by site, sex ( $\geq 25\%$  women) and age category (50-59, 60-69, and 70+) with a conservative 20% dropout rate, resulting in 40 evaluable participants/group. The second randomization at week 16 and will also be balanced by initial randomization (2x2 factorial design). Aim 1 and 2 power calculations assume two-sided, 2-sample/paired *t*-tests for between/within group comparisons of the change from baseline with a 0.05 significance level. We assume conservative within subject correlations ( $\rho$ ) of 0.7 or 0.5 to estimate the standard deviation (SD) of the outcome change, larger correlations and repeated measures will result in additional power. The Aim 1 primary outcome is change in 400-MWT. We assume an effect size comparable to Toohey, an intervention comparing HIIT to CME among middle-aged (mean age 51, SD 12 years) cancer survivors that resulted in a mean (SD) difference of 97 (82) and 36 (68) meters in 6-minute walk distance among HIIT and CME, respectively. Using  $\rho=0.7$ , and a sample size of 40/group, we will have  $>88\%$  power to detect a comparable *between* group differences of 45 (38) and 20 (38) second improvement in 400-MWT in HIIT and CME, respectively. For reference, in our prior exercise study, PWH had a 25 second improvement in 400-MWT. This also provides  $>99\%$  and  $>81\%$  power to detect *within* group differences in the HIIT and CME arms. For morning and evening fatigue, we assume a baseline mean of 19(8) and 27(8) points, respectively ([name], unpublished data). With  $\rho=0.5$ , and a sample size of 40/group, we will have  $>80\%$  to detect a change of  $\geq 27\%$  and  $\geq 20\%$ , respectively. The primary Aim 2 outcome is change in State 3 respiration. Based on Robinson, we estimate a baseline mean (SD) of 580 (180) pmol  $O_2$ /min/mL using  $\rho=0.5$ . This provides  $>81\%$  power to detect a difference in the change of 50% (HIIT) and 30% (CME). The muscle substudy is considered exploratory, however, we anticipate adequate power. Using preliminary data, combining HEALTH+ exercise groups (N=24), provides  $>80\%$  power to detect a change of -8.7% in MRI-PDFF of HEALTH+ participants. For within exercise group (CME or HIIT) comparisons, a sample size of 12 provides  $>80\%$  power to detect a difference of -12.5%. For the CME versus HIIT change from baseline comparison, a sample size of 12 per group provides  $>80\%$  power to detect group differences of 9.8%. For the change in OxPhos, combining HEALTH+ exercise groups (N=24, 3 dropouts/group), provides  $>80\%$  power to detect an OxPhos change of 0.039. For within exercise group (CME or HIIT) comparisons, a sample size of 12 provides  $>80\%$  power to detect an OxPhos difference of 0.055. For the CME versus HIIT change from baseline comparison, a sample size of 12 per group provides  $>80\%$  power to detect group OxPhos differences of 0.056. For the change in aim 3, combining HEALTH+ exercise groups, a sample size of N=24 (3 dropouts/ group), provides  $>80\%$  power to detect a 21%  $\dot{V}O_2$  change in HEALTH+ participants. For within exercise group (CME or HIIT) comparisons, a sample size of 12 provides  $>80\%$  power to detect 33% change in  $\dot{V}O_2$ . For the CME versus HIIT change from baseline comparison, a sample size of 12 per group provides  $>80\%$  power to detect a 30% difference in the 16-week change from baseline.

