will examine potential group (and site) differences in demographics and health and baseline measures with two-sample t test (or Wilcoxon), ANOVA (or Kruskal-Wallis test) or Chi-square test where appropriate. Variables that differ by group will be adjusted in sensitivity analyses. We will conduct primary analyses under an intention-to-treat principle (all participants analyzed based on randomized conditions). The impact of any missing data will be mitigated by the use of mixed effects modeling with baseline covariates that are conceptually relevant and associated to consistency in data collection. In the presence of missing data, mixed effects models are fitted with all available data and provide unbiased estimates of model parameters, as long as the data are missing at random or conditionally at random (conditional on the covariates). If appropriate, we will employ imputation techniques. False discovery rate (FDR) will be used to justify multiple comparison. All tests will be two sided.

Our primary aim is to determine the efficacy of HIIT vs CME on improving cognitive function over time. In stage 1 (baseline to 4 months), a general linear mixed model with participant ID as random effect:  $\text{score} = \text{Group} + \text{Time} + \text{Group} \times \text{Time} + \text{Site}$  will be used first to examine whether there is a significant group difference, wherein the study site is controlled to adjust for potential site effects. The best model fit with Bayesian information criterion (BIC) will determine the variance-covariance structure in above model. The significant interaction term in above model indicates a significant difference between two trajectories/slopes, i.e., treatment effect. The group comparison on the mean changes will also be contrasted with t test for effect size. In stage 2 (4 to 7 months), a similar general linear mixed model will applied:  $\text{score} = \text{Group1 (HIIT vs CME)} + \text{Group2 (Coaching vs Control)} + \text{Group1} \times \text{Group2} + \text{Time} + \text{Group1} \times \text{Time} + \text{Group2} \times \text{Time} + \text{Group1} \times \text{Group2} \times \text{Time} + \text{Site}$ , where the time is from 4 to 7 months. The non-significant interaction terms will be removed from the final model. Given any potential group differences in demographics and health at baseline, a sensitivity analysis will be conducted including those unbalanced variables in above models.

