For exploratory analysis, sex-by-group interaction and/or race-by-group interaction will be included in above models to explore the potentially moderating effects, conducted according to the rigorous methods proposed by Hayes. Given significant treatment effects on cognitive function, a PATH analysis will be conducted to explore the potential mediation effects of biomarker changes on cognitive function. We will also examine whether changes in parent R01 outcomes (e.g., VO2, physical function, fatigue) mediate cognitive changes. The exploratory blood markers will be obtained at baseline, 4- and 12 months, while the MRI neuroimaging markers will be obtained at the UAB site at baseline and 4 months. The group difference of biomarkers will be evaluated using a similar linear mixed regression model:  $\text{scores} = \text{Group} + \text{Time} + \text{Group} \times \text{Time}$ , where the group difference on slopes and mean changes will be contrasted.

Our secondary aim is to examine psychological MoA of adherence to habitual PA at 12 months. We will examine distal predictors (i.e., sociodemographics, physical health, intervention type [HIIT vs CME and coaching vs control], changes in parent R01 outcomes [e.g., weight loss, physical function, fatigue] using laboratory and survey data, and proximal psychological predictors using EMA (e.g., self-efficacy, perceived benefits, motivation, social support). First, we will use a linear mixed regression with random intercept:  $\text{PA} = \text{Predictor} + \text{Time} + \text{Predictor} \times \text{Time} + \text{Site}$ , to examine the association between PA adherence and each of the predictors of interest, adjusting for study site. Secondly, we will conduct a multiple linear mixed regression with random intercept and all significant predictors detected above as fixed effects to examine the covariate-adjusted association between PA and predictors:  $\text{PA} = \text{Time} + \text{Predictor1} + \text{Predictor2} + \dots + \text{Site}$ . The time-by-predictor interactions will be evaluated and removed from the model if not significant. The variance-covariance structure (e.g., AR1) in above models will be determined by the best model fit measured by Bayesian information criterion (BIC).

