## STUDY TIMELINE

We propose a 5-year timeline to accomplish our specific aims (**Table 1**). By conducting a rigorous, prospective, randomized clinical trial testing two exercise regimens, we will overcome limitations of previous studies investigating non-pharmacological approaches to improving the *healthspan* of people living with HIV. This design enables us to characterize the clinical (i.e., physical function and patient-reported fatigue) and translational (i.e., mitochondrial bioenergetics) effects of these interventions in an understudied, yet growing, population. To ensure that we meet enrollment and data collection milestones, we anticipate 4.5 full years of research procedures, with the remaining 6 months to finalize data analyses and disseminate the final study results.

R01 Cognitive substudy (HEALTH-COG) will leverage newly enrolled participants at the two sites of the parent HEALTH study (R01AG066562), add a University of Alabama at Birmingham (UAB) site, add new measures (psychological mechanisms of adherence, cognitive function, biomarkers) and a 12 month follow-up. This study is optional (to UCD/UW participants) and open to anyone enrolled in the parent HEALTH study. The sub-study R01 proposes to enroll/randomize 110 participants (UAB=60, University of Washington (UW)/University of Colorado Denver (UCD)=50 total between the two sites). Based on current enrollment numbers at the parent study sites (UCD=37 and UW=31), we anticipate it will be feasible for the new R01 to enroll the remaining participants across both sites (~32 participants), and due to timing of funding in relation to enrollment at UCD and UW, approximately 8-10 additional participants at both UCD and UW will need to enroll to meet and overall goal of 110 in this sub-study. The parent study end date is ~2 years into new R01 (yielding 2-3 additional years of study).

| Table 1.               |     |                      |   |
|------------------------|-----|----------------------|---|
| Timing
(Year/Month) |     | Enrollment
Target | Milestones  |
| Year 1                 | JIT |                      | 
 
Protocol & Manual of procedures finalized
 
IRB approvals
 
Hospital/research center approvals
 
Data transfer agreements between UCD-AMC and UW finalized and executed
 
  |

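### Cognitive Aim 2 picks predictors of 12-month physical activity by single-predictor significance, refits them on the same data without a fixed adjustment set, and does not say whether the promised FDR control covers the screen

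*Combined protocol and SAP*

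**What the plan says.** Aim 2 of the cognitive substudy (Cognitive Substudy Aims) is to "Determine MoA of long-term PA maintenance at 12 months after a 4 month supervised HIIT or CME intervention". The Cognitive Substudy Statistical Analysis treats this as the substudy's secondary aim, in two steps.

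- **Screen.** A random-intercept mixed model with predictor, time, their interaction and site is fitted for one predictor at a time, "to examine the association between PA adherence and each of the predictors of interest, adjusting for study site".
- **Refit.** The analysts will then "conduct a multiple linear mixed regression with random intercept and all significant predictors detected above as fixed effects". Time and site are always in this model. Predictor-by-time interactions are dropped if not significant.

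The significant distal predictors also become the covariates of the later ecological momentary assessment (EMA) models.

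On multiplicity, the same section says once, for the substudy as a whole, "False discovery rate (FDR) will be used to justify multiple comparison", and then "All tests will be two sided". It gives no family of tests, q level or stage. It also gives no list or number of candidates, no alpha for the screen, and no hold-out sample, cross-validation or penalisation. Exploratory Outcome Measures, item 22, lists psychological mechanisms of adherence at 48 weeks as an exploratory outcome.

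**The concern.** Two problems follow from the stated rule.

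First, a predictor enters the joint model because it was significant in these data, and is then tested again in the same data. Its second p-value and interval are computed as if it had been chosen in advance. Chance findings tend to stay significant, and true effects tend to look too large.

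Second, the adjustment set is left to the same screen. HIIT/CME and coaching/control are among the candidates. Either can change both a psychological score at 12 months and PA at 12 months, which makes it a common cause of the two. Age and sex can do the same. Under the rule, any of these is left out if it misses significance alone, however much it confounds the associations that remain.

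The result is a list of predictors that readers will take as the answer to the aim, and part of that list is passed on to the EMA models. How far it can be trusted depends heavily on where FDR is applied, and the text leaves that open.

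**Working it through.** The documents state no error rate, power or sample size for this analysis, so there is no planned figure to reproduce. The check asks how often the procedure yields a significant predictor when none is related to PA.

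**Inputs**
- Sample size: "The sub-study R01 proposes to enroll/randomize 110 participants" (Study Timeline). The parent trial's power section plans "with a conservative 20% dropout rate". Assuming the same loss here, 110 × 0.80 = 88. Both 88 and 110 were used.
- Alpha: 0.05 is assumed. The documents state it only for parent Aims 1 and 2, "for between/within group comparisons of the change from baseline with a 0.05 significance level".
- Candidates: an assumption counted from the named measures. Distal: 4 sociodemographic + 1 physical health + 2 randomised factors + 4 change scores = 11. Psychological: self-efficacy 1 + BREQ-3 subscales 5 + EMI-2 subscales 6 + self-regulation 1 + decisional balance 1 + social cohesion 1 = 15. Total 26. One score per construct gives about 17; scoring all subscales gives about 39.

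**Screen alone, independent null predictors:** P(at least one passes) = 1 − 0.95^m.
- m = 11: 0.431
- m = 17: 0.582
- m = 26: 0.736 (expected false passes 26 × 0.05 = 1.3)
- m = 39: 0.865

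**Screen plus refit, by simulation.** All predictors are null. Each is screened, the survivors are refitted together on the same data, and a run counts if any final p<0.05. Ordinary linear models stand in for the random-intercept model. The first three rows have N=88 (4,000 runs per setting), the last N=110 (3,000 runs), all with 26 candidates sharing one common correlation.

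| N, correlation | No FDR | BH on survivors only | BH over full screen |
|---|---|---|---|
| 88, 0 | 0.71 | 0.65 | 0.055 |
| 88, 0.3 | 0.43 | 0.38 | 0.055 |
| 88, 0.5 | 0.25 | 0.23 | 0.039 |
| 110, 0 / 0.3 / 0.5 | 0.71 / 0.42 / 0.25 | 0.65 / 0.37 / 0.24 | 0.048 / 0.040 / 0.036 |

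**Sensitivity (N=110, 26 candidates)**
- Correlation among all 26 of 0.6 gives 0.17 without FDR, and 0.8 gives 0.10.
- If only the 15 psychological scores are correlated (0 to 0.8), the rate without FDR is 0.72 down to 0.45, and with BH over the screen 0.054 down to 0.036.
- For a psychological score specifically, with that block correlated at 0 / 0.3 / 0.6, the rate without FDR is 0.48 / 0.33 / 0.15.
- If the predictor-by-time term also counts as a pass (2 × 26 = 52 tests), same correlations, the rate without FDR is 0.93 / 0.85 / 0.74. With BH over all 52 it is 0.052 / 0.048 / 0.035.

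**What FDR on the screen does not cure.** With 26 independent candidates, N=88 and a true effect of 0.20 SD, the refitted estimate among runs that survived a BH screen averaged about 0.37. The nominal 95% interval covered 0.20 in about 76 to 78% of those runs. BH limits false entries; it does not make the refit's estimates or intervals valid.

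**The case against.** The strongest reply is that FDR control is already promised, in the same section and without limitation to one aim, and that a series of one-predictor tests is its natural family. On that reading the null rate is about 2 to 5%. This stands as a fair reading. A reader might infer from the two-step rule that 25 to 70% of null trials would report a chance mechanism of adherence. The documents do not support that as an unconditional statement: it needs FDR to be absent or confined to the survivors, which the text neither says nor rules out.

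Other replies also have weight.
- The count of 26 is not in the documents. If the psychological scores are reserved for the EMA models and only the distal predictors are screened, it is about 11.
- About 11 of the 26 are age, sex, arm and similar, so calling every survivor a mechanism would be wrong.
- A common correlation of 0.5 across all candidates is not realistic when two of them are randomised factors.
- The plan describes this step as examining associations. Its mediation analyses are framed as estimation, and the arm effects on PA are examined elsewhere, in those analyses and in parent Aim 3.
- Null covariates carried into the EMA models cost some precision rather than creating false effects.

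None of this answers the reuse of the data or the loss of confounders from the joint model. Both follow from the stated rule even if FDR governs the screen.

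**Conclusion.** The concern holds in a limited form. The joint model will give selection-distorted and possibly under-adjusted associations however FDR is applied. Its false-positive rate depends on one unstated choice: with 26 candidates, roughly 25 to 70% (correlation 0.5 down to 0) without FDR or with FDR on the survivors only, against about 2 to 5% with Benjamini-Hochberg over the whole screen.

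These figures rest on an assumed count (17 to 39 is plausible), alpha 0.05, N of 88 to 110, and linear models in place of the mixed model. The 25 to 70% is not a bound: stronger correlation among all candidates lowers it, and counting interaction terms raises it.

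It would also be too strong to say that this threatens the trial's conclusions. It affects one exploratory substudy outcome and leaves the 400-m walk comparison untouched.

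**What to change.** Amend the Cognitive Substudy Statistical Analysis before the 12-month data are analysed.

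1. List every candidate predictor and how each scale is scored.
2. State that Benjamini-Hochberg at q=0.05 applies across all single-predictor tests, including the predictor-by-time terms, and that claims rest on those adjusted results.
3. Fit the joint model with a fixed core kept whatever its significance: HIIT/CME, coaching/control, site, age and sex. Add baseline PA only where it is collected. The Study Measures by Site table leaves actigraphy blank for UAB, which is to supply 60 of the 110 participants, so baseline PA cannot be a required term as the plan stands.
4. Report the joint model as descriptive, post-selection estimates and not as a second significance test. Its intervals remain conditional on the selection and should be labelled so.
5. Use the same fixed core as covariates in the EMA models, in place of whichever distal predictors were significant.

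The cost is SAP wording and little analysis time, with no new data or visits. Fewer predictors will be declared significant, and the core uses a few degrees of freedom.

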| Motivations  | Lab: 19-item Behavioral Regulation in Exercise Questionnaire (BREQ-3)  assesses Amotivation (four items), External Regulation (four items), Introjected Regulation (three items), Identified Regulation (four items), and Intrinsic Regulation (four items). Participants asked "Why do you engage in exercise?" and rate how true each statement is for them using Likert scale (e.g., "I exercise because it's fun").
Lab and EMA: 37-item Exercise Motivations Inventory (EMI-2)  assesses intrinsic and extrinsic motives to exercise. Participants indicate how true each statement is for them using Likert scale, with the following subscales: Health & Fitness, Social/Emotional, Weight Management, Stress Management, Enjoyment, Appearance. EMA in am; items use word "today"; items only include general item for each 6 subscale domains (e.g., "If I exercise today, it will be for... Health and Fitness"). |
| Self-Regulation Strategies                                     | Lab and EMA: 12-item Physical Activity Self-Regulation scale (PASR-12)  measures use of six strategies including self-monitoring, goal setting, eliciting social support, reinforcement, time management, and relapse prevention. Participants asked to rate how often they used each self-regulation strategy in the past 4 weeks on a Likert scale. EMA in pm; items use word "today" (e.g., "When I exercised today, I rearranged my schedule to ensure I had time for PA"). If no PA is reported, measure is skipped.   |
| Outcome Expectations   | Lab and EMA: 16-item Decisional Balance (DB) Scale for Exercise  assess positive and negative outcome expectations and includes 10 pros (e.g., "I would feel less stressed if I exercised regularly") and 6 cons ("Regular exercise would take too much of my time"); DB score is pros minus cons. EMA in am; items use word "today".  |
| Affective States   | EMA: 12-item Exercise-induced Feeling Inventory (EFI)  captures four feeling states: revitalization (e.g., energetic, refreshed), tranquility (e.g., calm, relaxed), positive engagement (e.g., enthusiastic, happy), and physical exhaustion (e.g., fatigued, tired). Four additional items  included to assess negative affect (e.g., anxious, stress, sad). EMA in am, pm, and PA event contingent.   |

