For EMA data, a linear mixed regression model including random effects for subject and day (within-subject) to account for the multilevel structure of the data will be used to examine the time-lagged effects of MoA variables occurring during a specified time interval (T-1) on PA during the subsequent (lagged) time interval (T) within each day of monitoring:  $\text{PA}(T) = \text{MoA}(T-1) + \text{Time of Day} + \text{Day} + \text{site} + \text{covariates}$ . The time interval T can be time of day or different days, for example we can use the MoA in Day 1 to predict the PA in Day 2 or use the MoA in the morning to predict the PA later in the same day. The covariates include significant distal predictors. Moderating effects will be explored by including interaction terms in above model. Concurrent effects of these MoA variables on PA (i.e., both the predictor and outcome were assessed during the same time interval) will also be examined. To explore whether the MoA variables mediate intervention (HIIT vs CME and coaching texting vs control) effects on PA, mediation analyses with focus on effect estimation rather than hypothesis testing will be conducted using path analysis with methods considering the multi-level nature of data and robust to non-normality (e.g., cluster bootstrapping), assuming a causal chain of the form: Intervention (HIIT vs CME) --> effect on MoA [as mediator] --> effect on PA. Using the estimated path coefficients, direct, indirect, and total effects will be estimated and uncertainty on these estimates be estimated computed in the form of confidence intervals. Using similar mediation approaches, we will also examine whether cognitive differences between groups at 12 months are mediated by differences in PA adherence at 12 months.

Quantitative feasibility, acceptability, and intervention fidelity outcomes will be compared across sites and exercise type using analysis of variance or chi-square tests when applicable.

Qualitative analysis will be conducted for acceptability questions at 4 months and PA barriers and facilitators at 12 months. [name] and [name] have a history of designing and analyzing data from qualitative studies. Content analysis will be used to derive themes related to barriers and facilitators to long-term PA, which will be synthesized with quantitative data to examine correlates (e.g., demographics, health).

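### The EMA lag model does not adjust for activity before the mechanism report, so for scores that can reflect exercise already done, the day-to-day coefficient may show carry-over of activity

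*Combined protocol and SAP*

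**What the plan says.** The model is in the Cognitive Substudy Statistical Analysis, in the paragraph on EMA data. PA in interval T is regressed on MoA in interval T-1, time of day, day, site and covariates, with random effects for subject and for day within subject. The model "will be used to examine the time-lagged effects of MoA variables" on later activity. The lag may run from morning to later the same day, or across days: "for example we can use the MoA in Day 1 to predict the PA in Day 2".

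On covariates the plan says "The covariates include significant distal predictors". The Cognitive Substudy Aims explain the term: "Distal predictors include sociodemographic (e.g., race, age, sex, education), clinical (e.g., physical health), and intervention factors". The analysis section adds changes in parent-trial outcomes. These are all person-level.

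The same paragraph plans a mediation analysis, "assuming a causal chain of the form: Intervention (HIIT vs CME) --> effect on MoA [as mediator] --> effect on PA", and a separate analysis of concurrent effects. It plans no model in the reverse direction, from PA to MoA.

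The Cognitive Substudy methods section sets 7 days of twice-daily prompts after the 12-month visit, with actigraphy worn for 7 days. In the table of mechanism measures, the self-regulation item is asked in the evening, refers to exercise done that day, and is skipped if there was none. The affect scale is timed as "EMA in am, pm, and PA event contingent". Self-efficacy and social interaction are asked morning and evening. The EMA motivation and decisional-balance items are morning only.

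**The concern.** A score collected in the evening, or triggered by activity, can be a consequence of exercise already done that day. That exercise may also predict the next day's, upward if people exercise in streaks and downward if they alternate days. Earlier activity is then a common cause of the Day 1 score and of Day 2 activity, and the lagged coefficient carries both paths.

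The random effects do not remove this. The subject effect takes up stable differences between people, but not day-to-day carry-over. With one PA value per day, a day-within-subject effect cannot be separated from the residual. The planned false discovery rate control deals with multiplicity, not with bias.

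These coefficients are the short-interval evidence on what sustains activity, the subject of the substudy's second aim. Reverse influence is the main rival explanation, and the model as written cannot tell it from an effect of the mechanism.

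**Working it through.** The documents give no power, effect size or autocorrelation for the EMA analysis, so there is no stated figure to reproduce. The check is a reading of the model plus simulation.

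**From the documents:** 110 participants (Study Timeline); 7 days of EMA; two-sided tests; no prior-PA term. A sample of 88 is also used: 110 x 0.8, borrowing the parent trial's 20% dropout.

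**Assumed:** PA variance 1; person-level share (ICC) 0.5; within-person day-to-day autocorrelation phi; MoA response to same-day PA g = 0.3 or 0.5; MoA noise SD 0.8.

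**Generating model, with no true effect of MoA on later PA:**
- PA(i,t) = b(i) + e(i,t), where e follows a first-order autoregression with coefficient phi.
- MoA(i,t) = u(i) + g x PA(i,t) + noise.

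**Expected bias.** In a long series with person effects removed, the slope of PA(T) on MoA(T-1) is g x phi x Vw / (g^2 x Vw + Vn), with Vw = 1 - 0.5 = 0.5 and Vn = 0.8^2 = 0.64. For g = 0.5 and phi = 0.4 this is 0.5 x 0.4 x 0.5 / (0.25 x 0.5 + 0.64) = 0.100 / 0.765 = 0.13. With g positive, its sign is that of phi. Given PA(T-1), the rest of the within-person variation in MoA(T-1) is noise, so the slope is zero.

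**Planned random-intercept model, N = 110**, share with |z| > 1.96 (1,000 runs per setting for phi of 0 or more, 500 for negative phi):

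| phi | g = 0.3 | g = 0.5 |
|---|---|---|
| -0.4 | 45% | 84% |
| -0.2 | 13% | 32% |
| 0 | 5% | 7% |
| +0.1 | 10% | 18% |
| +0.2 | 20% | 40% |
| +0.3 | 33% | 67% |
| +0.4 | 45% | 84% |

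The mean coefficient is negative for negative phi. For phi of 0.1 to 0.4 it is 0.021 to 0.059 (g = 0.3) and 0.033 to 0.091 (g = 0.5). It is smaller than the long-series value because the series is short and the random intercept only partly removes person effects. At N = 88 the rates for phi of 0.1 to 0.4 are 9% to 75%. With g = 0 and phi = 0.3 the rate is 5.5%, as it should be.

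**Sensitivity to the person-level structure.** Letting the person-level MoA trait be unrelated to PA widens the range: about 15-100% at phi -0.2 to -0.4, 7-83% at +0.2 to +0.4, and 7-33% at zero. Zero autocorrelation is therefore not always safe, because the short series adds its own bias.

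**Forms of the correction:**
- Raw PA(T-1) added to the random-intercept model: 4-7% under the structure in the table, but up to 76% when the MoA trait is unrelated to PA.
- MoA centred but PA(T-1) left raw: mean coefficient about -0.05 to -0.14, and rates of 20% to 94%.
- MoA and PA(T-1) both person-mean centred: 3-8% in every setting.

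**The case against.** **Not every scale is exposed.** The strongest objection is that morning-only motivation and decisional balance precede most of that day's activity, which therefore cannot cause them and may mediate their effect on the next day. Adding same-day activity there would remove part of the effect being studied. This stands. A reader might infer that every lagged analysis needs the whole previous interval's PA, but the measurement schedule does not support that.

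**The same-day lag is safer.** Morning MoA precedes later same-day PA, so only carry-over from the previous day remains. This also stands, and the simulations cover daily lags only.

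**Strong negative autocorrelation is not documented.** The three-sessions-a-week schedule belongs to the 16-week supervised phase, while the EMA follows the 12-month visit, when exercise is self-directed. A reader might infer that alternate-day exercise makes a false finding nearly certain. The documents do not establish that pattern. Error rates from person-demeaned regressions also should not be applied to the planned mixed model, because demeaning over 7 days adds a negative bias of its own.

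**The plan leaves room.** The covariate list is not closed, and an AR1 structure is mentioned. But nothing commits to prior activity, and the AR1 wording refers to the models set out before the EMA paragraph.

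**The stakes are limited.** This is a secondary aim of a substudy that is optional at two sites, it is listed among the exploratory outcomes, and the mediation analysis emphasises estimation over testing. That limits the priority. It does not remove the bias, which affects estimates as well as tests.

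**Conclusion.** The point holds for Day 1 to Day 2 models that use evening or activity-triggered scores. As written, the coefficient cannot separate an effect of MoA on later PA from carry-over of earlier PA, and it can be significant with either sign when there is no effect. In weaker form, morning scores can carry over the previous day's activity.

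The size is not known for this trial. Over the assumed range (N = 110, 7 days, phi -0.4 to +0.4), false-positive rates go from about 7% to over 80%, and are close to nominal in some settings near zero autocorrelation. They depend on the PA autocorrelation, the strength of the MoA-PA link and the person-level structure, none of which the documents give. The percentages are illustrations and should not be read as forecasts.

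A reader might also infer that the trial's main result is in doubt. It is not: the 400-m walk analysis does not use this model.

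**What to change.** In the EMA paragraph, add as a covariate the actigraphy activity in the interval before the MoA prompt, defined by scale:
- **Evening or event-triggered scores in a next-day model:** the same day's activity up to the prompt.
- **Morning scores, in same-day or next-day models:** the previous day's activity. Do not adjust for activity after the prompt, which may be a mediator.

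Enter both MoA and prior PA person-mean centred, or fit a multilevel autoregressive model in Mplus, which the substudy analysis already names. State this explicitly, because raw prior PA can leave or worsen the bias. It would also help to report the reverse model (PA to later MoA) alongside, and to treat the self-regulation item separately, since it is missing by design on days without activity.

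The cost is SAP wording and modest extra modelling. Morning-score models lose the first day. Evening next-day models lose nothing further, because lagging MoA already drops the first outcome day. The prior-PA coefficient itself carries short-series bias and should not be interpreted.

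The by-site table of study measures marks actigraphy for UW/UCD but not for UAB, which is to supply 60 of the 110 participants. The substudy methods have it worn for 7 days. These must be reconciled, since both the outcome and the added covariate need it.
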